Improving Resilience and Longevity for Workers Through Exercise Protocol

The Canadian workforce is aging. The most prevalent age group is 50-54 years and most of these Canadians will aim to continue working over the next 10 years¹. However, the impact of arthritis on aging Canadians compromises their ability to continue working². By 2031, over 2 million Canadians aged 45 to 64 years will have arthritis. Among those with arthritis, one of three is expected to be out of work³. This unemployment rate is worse than for any other chronic health condition³.

We aim to boost the ability of older adults with the most common arthritis, osteoarthritis (OA), to engage in the workforce for as long as they desire. Osteoarthritis targets older adults and currently affects 4.4 million Canadians, a number expected to grow to 10 million in the next two decades⁴. The disease causes degeneration of all joint tissues, most commonly in the knee and hip⁵. Further, OA affects the Canadian labour force: 30% of those with OA will experience difficulty at work⁴. Pain and immobility caused by OA result in frequent absences from work and, ultimately, lost productivity⁶.

Identifying strategies to promote productivity among older workers with knee and hip OA will be of great public health significance in the coming decades. However, we face two challenges. First, obesity among sedentary workers is a risk for worsening knee and hip OA. A five unit increase in body mass index is associated with a 35% increased risk of developing OA⁷. Second, large occupational loads on the knee and hip worsen OA. Pooled data from 66 studies (n=526,343) revealed that, compared to workers who stand, those required to frequently squat, kneel, and carry have over a 60% increased risk of worsening chronic pain⁸. Therefore to promote productivity, we must address obesity while minimizing exposure to large loads. Unfortunately, few studies have investigated strategies to improve productivity among aging workers with OA⁹. A systematic review showed that exercise has the most promise in achieving this goal because it reduces pain and sick time, and improves mental health⁹. By comparison, ergonomic interventions (e.g., mechanical patient lifts, ergonomic work-stations), and education yield a minimal effect on pain, sick time, or longevity in the workplace⁹. Not surprisingly, there is a call for studies examining exercise for the aging worker with knee and hip OA⁹.

RESEARCH PURPOSE AND SCOPE

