Randomization: An independent research assistant will conduct randomization and concealed allocation. Participants will be randomized to receive either the exercise intervention, or no intervention. After baseline, the independent research assistant will provide each participant with one sequentially numbered, sealed, opaque envelope that identifies the intervention they will receive.

Interventions

Exercise Program: A 12-week exercise intervention will be offered in the workplace. Ford employees will complete their exercise program at Ford in the on-site exercise facility. 20 of the 40 participants will be randomized to the exercise intervention.

A 12-week supervised exercise program designed for OA knees and hips will emphasize strengthening leg muscles with minimal loads. Each exercise program will be 30 minutes and offered at 7:00am (Mon, Tues, Wed, Thurs, Fri). These timeslots will enable participants to exercise at the start of their workday. Participants will be asked to attend 3 or more supervised exercise sessions weekly ¹⁸. Strengthening will focus on "body weight" strategies that we have used previously, such as squats and lunges. A certified yoga instructor will offer exercise modifications and education about anatomy, OA, and proper lower limb alignment. Over 12 weeks, the exercises will be progressed. These exercises yield nominal loads while increasing leg strength ¹⁹. Our previous randomized controlled trial of this intervention (n=31), delivered within the community, yielded improvements in pain, mobility and self-reported physical function without adverse events.

Control Program: 20 of the 40 participants will be randomized to the control group. These participants will be asked to refrain from changing any interventions or activity existing at baseline over the 12-week intervention period. Afterwards, these participants will be offered the same exercise program free of charge.

Outcome Measures

Outcome measures will be collected at baseline and immediately after the 12-week exercise program.

Primary Outcome: The primary outcome is the change between baseline and follow-up on the LEFS ^{16, 20, 21}. The LEFS consists of 20 items on an adjectival scale that assess difficulty during mobility tasks ranging from transfers to running. This range avoids ceiling and floor effects. It is reliable and valid in OA and has superior sensitivity to change compared to similar measures ^{17, 21, 22}.

Secondary Outcomes

- *Pain:*

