 - The Work Ability Index (WAI) is a widely-used self-report questionnaire that consists of seven dimensions including current work ability relative to life-time best, work ability related to job demands, number of current physician-diagnosed health conditions, estimated work impairment due to the conditions, sick leave over the past year, own prognosis, and mental resources ³⁹. The WAI produces reliable data ³⁹.
 - Depressive symptoms will be assessed with the Center for Epidemiologic Studies—Depression (CES-D) Scale, a 20-item scale with emphasis on affect (mood, guilt, worthlessness, helplessness, appetite) ⁴⁰. Data from the CES-D are valid and reliable in adult and arthritic populations ⁴⁰⁻⁴².
 - Self-efficacy will be measured using the Arthritis Self-Efficacy Scale (ASES). The ASES measures arthritis-specific beliefs regarding perception of performance on certain tasks to cope with the disease ⁴³. The ASES produces both reliable and valid data in knee OA ⁴⁴.

Statistical Analyses: Descriptive statistics will be calculated. A repeated measures analysis of variance will be used to compare the impact of the exercise program on change scores for each outcome measure between the exercise and control groups. Independent analyses will be performed for participants that demonstrated clinical criteria for hip and knee OA.

References

1. Canada S. Population by sex and age group. 2013; <http://www.statcan.gc.ca/tables-tableaux/sum-som/l01/cst01/demo10a-eng.htm>. Available at. Accessed May 15 2014, 2014.
4. Canada AAo. *The impact of arthritis in Canada: Today and over the next 30 years*. 2011.

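### Does the Work Ability Index's past-year sick-leave item, asked after only 12 weeks, call for a separate absence measure?

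*Combined protocol and SAP*

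**What the plan says.** The WAI appears under Secondary Outcomes, in the Resilience group, beside the resilience, depression and self-efficacy scales. It is described as follows: "The Work Ability Index (WAI) is a widely-used self-report questionnaire that consists of seven dimensions". The later dimensions in that list are "estimated work impairment due to the conditions, sick leave over the past year, own prognosis, and mental resources". No absence diary, employer record or shorter recall period is named anywhere else.

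On timing, Outcome Measures states: "Outcome measures will be collected at baseline and immediately after the 12-week exercise program". Under Randomization, allocation is revealed only once baseline is complete: "After baseline, the independent research assistant will provide each participant with one sequentially numbered, sealed, opaque envelope". Statistical Analyses specifies one method throughout: "A repeated measures analysis of variance will be used to compare the impact of the exercise program on change scores for each outcome measure".

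The statement of purpose names four outcome domains: mobility, pain, physical capacity and resilience. Sick time appears only in the opening background, where a cited systematic review is summarised as showing that "exercise has the most promise in achieving this goal because it reduces pain and sick time, and improves mental health".

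**The concern.** A one-year look-back asked 12 weeks after randomisation covers mostly time that the intervention could not have influenced. The background gives reduced sick time as one reason to expect exercise to help, and this dimension is the only place where a reader could look for evidence of it. If the item barely moves because most of its window is fixed history, a null result might be taken to show that exercise does not affect absence.

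Recall sharpens the worry. Each participant reports a year-long total twice. Errors in those totals grow with a year of absence, while any treatment effect can come from 12 weeks only. A question limited to the previous 12 weeks would avoid that mismatch at little cost.

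**Working it through.** The plan gives no power, precision or expected value for sick leave or for the WAI, so there is no stated figure to reproduce.

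**Inputs from the documents.** Look-back one year, taken as 52 weeks (Secondary Outcomes, Resilience). Programme 12 weeks, with assessment at baseline and immediately afterwards (Interventions; Outcome Measures). Allocation after baseline (Randomization). Twenty per arm (Interventions). Analysis of change scores (Statistical Analyses).

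**Inputs assumed.** The documents do not give the item's response format, so day counts are assumed. Also assumed are 8 sick days a year, a 50% reduction during the programme, 2-day spells, Poisson spells with gamma between-person rates (shape 1), and lognormal recall error with a coefficient of variation (CV) of 0, 20 or 40%, independent across visits.

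**1. Share of the look-back before randomisation.**
(52 − 12)/52 = 40/52 = 76.9%.
If the programme starts 4 weeks after randomisation (an assumption), (52 − 16)/52 = 69.2%.

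**2. What the change score retains.** Split the baseline year into its oldest 12 weeks (A) and the remaining 40 (B), and let C be the 12 programme weeks.
Baseline total = A + B. Follow-up total = B + C. Change = C − A.
With exact recall in raw days, B drops out and the full effect of the programme weeks stays in the between-arm difference:
0.5 × 8 × 12/52 = 0.92 days.
The overlap alone therefore neither biases the comparison nor shrinks the effect in days. Only recall error that differs between visits leaves noise from B.

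**3. Size of the noise.** Simulation with 20 per arm, two-sided 0.05, 6,000 runs per setting:

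| Measure | Power, CV 0 | Power, CV 20% | Power, CV 40% |
|---|---|---|---|
| Past-year total, change score | 18.3% | 10.5% | 6.4% |
| 12-week count, change score | 18.0% | 17.6% | 14.2% |
| 12-week count, adjusted for baseline count | 26.8% | 25.8% | 22.1% |

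The first and third rows differ in two respects: the window and the analysis. The first two rows isolate the window. On that comparison it makes no difference with exact recall, and costs about 7 to 8 percentage points with recall error (17.6 − 10.5 = 7.1; 14.2 − 6.4 = 7.8).

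**4. Sensitivity to independent recall errors.** The same person recalls the shared 40 weeks twice, so some persistence of over- or under-reporting is plausible, and persistent error largely cancels in a change score. With an error correlation of 0.5, past-year power is about 12% at CV 20% and 8% at CV 40%. With a correlation of 0.95 it is about 17% and 13%. The 12-week change score gives about 16 to 18% at CV 20% and 14 to 17% at CV 40%. At a correlation of 0.95 and CV 20%, the difference due to the window is gone.

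**5. Would the replacement make a null interpretable?** The approximate 95% confidence interval half-width is 2.02 × the standard deviation of the estimate.
Past-year change: 2.02 × 0.83, 1.34 and 2.23 = ±1.7, ±2.7 and ±4.5 days.
Adjusted 12-week count: 2.02 × 0.63, 0.66 and 0.72 = ±1.3, ±1.3 and ±1.5 days.
Every half-width exceeds 0.92 days. An estimate of zero from either measure would leave a halving of absence inside the interval.

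**6. Other assumed inputs.** At 16 sick days a year, the adjusted count has 42.2% and 33.2% power at CV 20% and 40%; at 4 days a year, 15.8% and 13.9%. A separate model with single-day absences and less between-person variation gives about 35 to 45% for a direct 12-week count at 5 to 8 days a year and a 50% reduction. None of these reaches even 50%.

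**The case for a change.** The best case for a change is that it costs one extra question per visit and buys real precision. At 20% recall error the adjusted 12-week interval is about half as wide as the past-year one (±1.3 against ±2.7 days), and at 40% about a third as wide (±1.5 against ±4.5). At 40% error, past-year power is barely above the 5% false-positive rate even though absence has been halved. Sick time is part of the rationale, and the plan does not warn against over-reading the dimension.

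Much of this stands. The 77% is correct, the WAI item is the only absence item, and a 12-week question would measure absence more precisely if recall errors are not strongly correlated across visits. What does not stand is the step to a defect in the plan. The harm requires someone to extract one of seven dimensions, test it alone and interpret a null, and the plan describes none of that. Part of the gain in precision comes from baseline adjustment and not from the shorter window. The main reason a null would say little is 20 participants per arm, which the extra question leaves as it is. It would also lengthen an already long secondary list with an outcome outside the stated domains. If the investigators decide to comment on absence, a 12-week question reported as an exploratory estimate with its interval would be a sensible option, but the present objectives do not need it.

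**Conclusion.** No change is needed. Using the WAI as a whole is a fair choice for a resilience and work-ability measure, and its one-year sick-leave item comes with it. About 77% of that item's look-back at follow-up precedes randomisation (69% with an assumed 4-week delay), but in a change score of days the shared weeks cancel except for recall error that differs between visits. Under the assumptions above, the window alone costs between nothing and about 8 percentage points of power, starting from a level under 20%. No planned result depends on it: absence is not a stated outcome, no analysis by dimension is described, the primary Lower Extremity Functional Scale comparison is unaffected, and the WAI total is not shown to be. The 77% follows from the documents. Every power and interval figure rests on assumed sick-day rates, effect size, response format and recall error. The conclusion does not depend on their exact values, because a null on absence with 20 per arm would be uninformative under either window across the range examined.

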The purpose of this study is to examine the impact of an OA-specific aerobic and strengthening exercise program, delivered within the workplace, on mobility, pain, physical capacity, and resilience among workers with knee or hip OA as well as those with no joint pain. We hypothesize that exercise designed for OA, delivered at work, will improve all of these outcomes.

METHODOLOGY

Participants

Participants will be women and men employed in administrative roles at Ford Motor Company in Oakville. All eligible participants will be welcome to participate.

Inclusion and Exclusion Criteria: We will recruit 40 participants from Ford. Inclusion criteria include part- or full-time employment in an administrative role at Ford. Men and women will be welcome. The exclusion criteria include a self-reported history of patellofemoral symptoms because the exercise program delivered to the intervention group places large loads on this joint. Participants with a previous osteoporotic fragility fracture will be excluded. Those with osteoporosis but no fragility fracture will be eligible. Exclusion criteria include active non-arthritis joint disease (e.g., gout); conditions that might be exacerbated (e.g., unstable angina); neurological conditions such as a stroke; leg trauma within 3 months; and cancer. Participants will be screened for the American College of

Rheumatology (ACR) criteria for clinical knee or hip OA. However, participants not meeting this criterion will still be eligible to participate.

Recruitment & Sample Size: Participants will be recruited through the research coordinator at McMaster. Administrative personnel at Ford who are not in a supervisory role (i.e., Fitness Centre Manager) will disseminate recruitment posters and an email/verbal script. Both will request that interested employees directly contact the research coordinator. These materials will explicitly state that the decision to participate, or not participate, will not be shared with Ford administration.

Our primary outcome is change in self-reported mobility on the Lower Extremity Functional Scale (LEFS). Self-reported mobility is critically important from the patient's perspective ¹³ and is likely to see the largest effect of exercise ¹⁴. The minimal clinically important difference (MCID) of the LEFS is 5 points ^{15, 16}. Rehabilitation produces changes of ≥ 10 LEFS points, with an effect size of 0.5¹⁷. Given a Type I error=0.05 on change, n=27 will yield 81% power.

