 - Six-Minute Walk Test (6MWT) - The 6MWT is used to quantify walking ability. The 6MWT is an inexpensive clinical tool that involves recording the distance that participants cover while walking indoors at their own pace for 6 minutes. Participants are free to stop or use a mobility aid to complete the walking task, making this measure clinically useful. The 6MWT measurement will be recorded indoors in a well-lit, tiled rectangular hallway. The score recorded is the total distance traveled in 6 minutes. Instructions for the 6MWT will correspond with the published protocol ³³. The 6MWT yields highly reliable (intraclass correlation coefficient=.96) and valid data ³⁴.
 - Stair Climbing - Participants will be asked to ascend and descend a 9-step staircase as quickly as possible, without compromising their safety. The hand rail can be used as needed. The participants will be asked to start at the base of the stairs at a distance from the first step of their choosing. The participants will be instructed not to run or jog, and not to skip any steps. Time to ascend and descend will be recorded separately, to the nearest 10th of a second, using a stopwatch. Participants will be asked to repeat this procedure two times, where scores from only the ascent and descent on the second attempt are recorded.

Data from our laboratory demonstrate excellent test-retest reliability of the stair ascent and descent tasks among 29 adults (ICC=0.881, 0.843 respectively).

- 30-Second Chair Stand Test - The 30 second chair stand task quantifies the number of sit-to-stand movements that can be completed within 30 seconds, starting from a seated position in an armless chair of a standard height (45 cm). After an opportunity to practice the task, participants will be asked to perform this task at a comfortable pace. Knee extensor strength is a strong predictor of performance on repeated chair stand tests ³⁵. In addition, lower extremity muscle power was predicted from performance of the 30 second chair stand in 14 older adults ³⁶.
- *Resilience*: To reflect the ability to adapt to stress and adversity, we selected measures of resilience, work ability, and depression.
 - The Resilience Scale (RS) is a 25-item questionnaire that captures information about personal competence and acceptance of life and self ³⁸. This questionnaire produces data that are reliable and show good concurrent validity ³⁸.

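### With only two visits, the planned repeated-measures ANOVA on change scores is an unadjusted t-test on change; adjusting for the baseline already collected would usually narrow the interval at very little cost

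*Combined protocol and SAP*

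**What the plan says.** The Statistical Analyses section contains the whole inferential plan: "A repeated measures analysis of variance will be used to compare the impact of the exercise program on change scores". This applies to every outcome and contrasts exercise with control. Separate analyses are planned for participants meeting clinical OA criteria. No covariate, effect estimate or interval is mentioned.

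Other sections fix the design:

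- The visits, under Outcome Measures, are two: "Outcome measures will be collected at baseline and immediately after the 12-week exercise program".
- The order of baseline and allocation is given under Randomization: "After baseline, the independent research assistant will provide each participant with one sequentially numbered, sealed, opaque envelope".
- The main endpoint is defined in terms of change: "The primary outcome is the change between baseline and follow-up on the LEFS".
- The arm sizes are under Interventions: "20 of the 40 participants will be randomized to the exercise intervention"; the other 20 are controls.
- Recruitment & Sample Size: rehabilitation is said to change LEFS by at least 10 points with an effect size of 0.5, the MCID is 5 points, and "Given a Type I error=0.05 on change, n=27 will yield 81% power".

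No LEFS SD and no baseline-to-12-week correlation is given anywhere.

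**The concern.** With one baseline and one follow-up value per person, a repeated-measures ANOVA adds nothing to a t-test on change. Subtracting the baseline in full amounts to fixing its regression slope at 1. When the true slope differs from 1, the change-score estimate stays correlated with whatever chance baseline difference randomisation leaves between two groups of 20. ANCOVA estimates the slope and removes that correlation.

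This is not bias, and the change-score standard error already includes it. The price is an interval that is usually wider than it need be, in a trial of 40 people where the covariate is already in hand. Because envelopes are handed over after baseline, the baseline value cannot be affected by knowledge of allocation and is a legitimate covariate.

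**Working it through.** **The plan's own figure.** The 81% reproduces by noncentral t as a one-sample (within-group) test on change, n = 27, effect 0.5, one-sided 0.05: 81.2%. Two-sided it is 70.6%. A two-sided comparison of 27 per arm gives 43.8%. The stated power therefore does not describe the randomised comparison. That is a separate and larger matter, and is noted here only so that the gain below is not mistaken for a remedy.

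**Equivalence.** In a simulated two-visit data set of 20 versus 20, the group-by-time F was 6.7611 and the squared t on change was 6.7611 (both p = 0.0132).

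**Inputs.** N = 40 and n = 20 per arm are from the protocol, taking all 40 as analysed. The correlation r and k = follow-up SD / baseline SD are assumptions: r from 0.3 to 0.9, k from 0.8 to 1.25.

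**Formulas**, per unit baseline variance:

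- Var(change) = (1 + k² − 2rk)(2/n)
- Var(ANCOVA) = k²(1 − r²)(2/n)(1 + 1/(N − 4)); the last factor is the cost of estimating the slope, 1 + 1/36 = 1.028
- Ratio = k²(1 − r²)/(1 + k² − 2rk) × (1 + 1/(N − 4))

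With k = 1 the ratio reduces to (1 + r)/2 × 1.028. At r = 0.5 that is 0.75 × 1.028 = 0.771, and 40/0.771 = 52 participants' worth.

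| k | r = 0.3 | r = 0.5 | r = 0.7 | r = 0.9 | ratio above 1 when |
|---|---|---|---|---|---|
| 0.8 | 0.52 | 0.59 | 0.65 | 0.63 | never |
| 0.9 | 0.60 | 0.69 | 0.77 | 0.83 | never |
| 1.0 | 0.67 | 0.77 | 0.87 | 0.98 | r above 0.95 |
| 1.1 | 0.73 | 0.84 | 0.95 | 1.03 | r from 0.81 to 0.96 |
| 1.25 | 0.81 | 0.92 | 1.01 | 0.98 | r from 0.68 to 0.88 |

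Simulation (40,000 runs, k = 1) gave 0.662, 0.776, 0.877 and 0.979, in agreement.

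**Bound on the loss.** (1 + k² − 2rk) − k²(1 − r²) = (1 − rk)² ≥ 0, so the ratio cannot exceed 1 + 1/(N − 4), which is 1.028 at N = 40. This takes the same r and k in both arms.

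**Performance tests.** The protocol states that "The 6MWT yields highly reliable (intraclass correlation coefficient=.96) and valid data" and that "Data from our laboratory demonstrate excellent test-retest reliability of the stair ascent and descent tasks among 29 adults (ICC=0.881, 0.843 respectively"). Reliabilities are not 12-week correlations. Used as r with k = 1, they give 1.01 (6MWT), 0.97 (ascent) and 0.95 (descent).

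**In LEFS points.** If the raw SD is 20 (an assumption, 10/0.5) and k = 1, the standard error of the group difference is 20√(2(1 − r)/10) for change scores and 20√((1 − r²) × 1.028/10) for ANCOVA:

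| r | change | ANCOVA |
|---|---|---|
| 0.3 | 7.48 | 6.12 |
| 0.5 | 6.32 | 5.55 |
| 0.7 | 4.90 | 4.58 |
| 0.9 | 2.83 | 2.79 |

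A chance baseline difference of one standard error, 20√(2/20) = 6.3 points, moves the change-score estimate by (1 − r) × 6.3 = 4.4, 3.2, 1.9 and 0.6 points at these values of r.

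**Power**, 20 per arm, two-sided 0.05, k = 1. If 0.5 is in change-score SD units, the noncentrality is 0.5√10 = 1.58 on 38 df for change scores: 34%. For ANCOVA it is 1.58/√ratio on 37 df: 47%, 42%, 38% and 34% at r = 0.3, 0.5, 0.7 and 0.9. If 0.5 is in raw SD units, change scores reach 80% from r of about 0.85 and ANCOVA from about 0.84.

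**OA-only analyses.** Their size is not stated. With assumed totals of 20 and 10, the maximum cost is 1/16 = 6.3% and 1/6 = 16.7%, and the break-even at k = 1 falls to r = 0.88 and 0.71.

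**The case against.** The strongest reply is that nothing here is broken. The protocol consistently chooses change as its outcome, the test is valid and unbiased, and the choice is between two valid estimators. That stands, and it is why this is an improvement and not a correction.

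The benefit in this trial is also unknown: across the table the ratio runs from 0.52 to 1.03. That stands too. The case for ANCOVA rests on the asymmetry between a possible gain of a third or more and a small maximum loss, not on a known r.

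Four narrower points have some force:

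- The baseline-imbalance shifts should not be set against the 5-point MCID as if they were bias. The standard errors are the fairer comparison, and there the saving is 1.4, 0.8, 0.3 and 0.03 points. These figures also depend on reading 20 as the raw SD.
- The 2.8% bound needs a common slope in both arms. With deliberately extreme slopes of 0.5 and 1.5, simulation gave a ratio of about 1.04, so the bound moves little.
- The cost is not negligible in a small OA-only subset, and some performance tests may gain nothing.
- The text does not name the tested term. Group-by-time is an inference, but it is the only sensible reading of a between-group comparison of change.

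None of this favours leaving the baseline out of the main analysis.

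**Conclusion.** The concern holds as a matter of efficiency. The planned analysis amounts to an unadjusted t-test on change: valid, but usually less precise than ANCOVA on the same data. With equal SDs and 40 analysed, ANCOVA reduces variance by about 33%, 23%, 13% and 2% at r = 0.3, 0.5, 0.7 and 0.9. The gain vanishes near r = 0.95, or whenever rk is close to 1. The worst case with a common slope is a 2.8% increase in variance. The algebra is certain; the size of the gain rests on an assumed r and assumed SDs. ANCOVA does not make the trial adequately powered if it was not so already. The change should be made, and before outcome data are seen, so that the choice of estimator cannot follow the results.

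**What to change.** Replace the repeated-measures sentence in Statistical Analyses with:

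> For LEFS and each secondary outcome, the 12-week score will be compared between randomised groups by ANCOVA with the baseline value of that outcome as covariate; the adjusted mean difference and 95% CI will be reported.

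The primary outcome need not change. With baseline in the model, using the 12-week score or the change as dependent variable gives the same treatment coefficient; only the baseline slope differs, by 1.

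Also state in advance which model the OA-only analyses use. Using ANCOVA there keeps one method throughout, at the larger slope cost shown above if the subset is small.

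The cost is one sentence, one degree of freedom and about 2.8% variance inflation at N = 40, with no new data.

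### The change-score ANOVA can use only participants with both LEFS scores, and the plan neither seeks week-12 LEFS from non-attenders nor states analysis by allocated arm

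*Combined protocol and SAP*

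**What the plan says.** The primary endpoint is defined under Outcome Measures: "The primary outcome is the change between baseline and follow-up on the LEFS". The same section fixes two assessment times and no interim one: "Outcome measures will be collected at baseline and immediately after the 12-week exercise program".

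The Statistical Analyses paragraph has three sentences. The first promises descriptive statistics. The second names the method: "A repeated measures analysis of variance will be used to compare the impact of the exercise program on change scores for each outcome measure", comparing the exercise and control groups. The third adds a subset: "Independent analyses will be performed for participants that demonstrated clinical criteria for hip and knee OA".

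On burden, the exercise arm has this request: "Participants will be asked to attend 3 or more supervised exercise sessions weekly". Sessions are at 7:00am on weekdays for 12 weeks. Controls have no sessions, are asked to keep their existing activity unchanged, and are offered the program free afterwards.

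The documents contain no analysis set, no statement of analysis as randomised, no rule for a missing week-12 score, no expected dropout rate, no instruction on follow-up of people who stop attending, and no sensitivity analysis. The paragraph is complete and runs straight into the reference list, so redaction does not explain the gap.

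**The concern.** A change score needs both measurements. Someone who stops exercising and does not return at week 12 has none and contributes nothing to the primary comparison. Nobody has to choose that exclusion, because it follows from the named method.

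Concealed randomisation protects the comparison at allocation but not against selection afterwards. The arms carry different burdens: at least 3 x 12 = 36 sessions in one and none in the other. Unequal loss is therefore possible. If those lost from the exercise arm are the ones who would have improved least, the completers' mean is too high, and a difference can appear where there is none. Without a sentence on analysis by allocated arm, nothing in the plan rules out excluding poor attenders later.

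**Working it through.** **1. The plan's own figure.** Recruitment & Sample Size states: "Given a Type I error=0.05 on change, n=27 will yield 81% power". With effect size 0.5, a one-sided one-sample t-test on change with n=27 gives power 0.812, so the figure reproduces in that form. It contains no dropout term. The gap between 27 and the 40 recruited, 13/40 = 32.5%, is not described as an allowance for loss.

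**2. Does the method drop people with one score?** With two time points, the group-by-time F equals the square of the two-sample t on change scores. A numerical check on simulated data (20 per arm) gave 2.486 both ways. Only people with a change score enter the contrast.

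**3. Size of the possible bias.** From the documents: 20 per arm and alpha 0.05. Assumed: no true effect, two-sided testing, loss in the exercise arm only, a share q lost, and correlation r between dropout and change. In SD units of change,

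shift = r x phi(z_q)/(1 - q), where z_q is the normal quantile at q.

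- q = 10%, r = 0.3: 0.3 x 0.1755/0.9 = 0.06
- q = 10%, r = 0.5: 0.5 x 0.1755/0.9 = 0.10
- q = 20%, r = 0.5: 0.5 x 0.2800/0.8 = 0.175
- q = 30%, r = 0.5: 0.5 x 0.3477/0.7 = 0.248

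Simulation with 40,000 trials per setting:

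| Loss, exercise arm only | r | Shift (SD of change) | Two-sided error |
|---|---|---|---|
| 10% | 0.3 | 0.06 | 5.3% |
| 10% | 0.5 | 0.10 | 6.1% |
| 20% | 0.3 | 0.10 | 5.9% |
| 20% | 0.5 | 0.17 | about 8% |
| 30% | 0.3 | 0.15 | 6.8% |
| 30% | 0.5 | 0.24-0.25 | about 11% |

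**4. In LEFS points.** The plan gives no SD. If its 10 points and effect size 0.5 refer to the SD of change, that SD is 10/0.5 = 20. Shifts of 0.17 and 0.24 SD are then 3.4 and 4.8 points, against the plan's MCID of 5. At an SD of 10 they are 1.7 and 2.4.

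**5. What baseline adjustment does** (assumed baseline-to-week-12 correlation 0.5).
- Precision: the standard error relative to the change-score analysis is sqrt((1 + 0.5)/2) = 0.866 in large samples. Simulation at 20 per arm gives about 0.88, so about 12% smaller.
- Loss driven by baseline, 4 of 20: the change-score contrast is off by about 0.16 SD, and the adjusted one by about 0.
- Loss driven by the change itself, r = 0.5: bias falls only from 0.17 to 0.13 SD (4 lost) and from 0.24 to 0.18 SD (6 lost). About three quarters remains.

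**6. What giving the missing exercise participants the control-arm change does.** With no true effect, the remaining bias is (1 - q) x shift: 0.8 x 0.17 = 0.14 SD and 0.7 x 0.24 = 0.17 SD. This is a partial check only.

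**The case against.** The strongest reply is that missed sessions are not missed scores. Outcome Measures attaches no attendance condition to the week-12 assessment, and the planned comparison is between groups that the Randomization section defines by allocation. On a natural reading everyone is measured and compared as allocated, and the participants are employees at the site completing a questionnaire. This stands to the extent that bias requires lost week-12 scores. It does not fill the gap, because the plan never says that scores will be pursued or that allocation governs the analysis.

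Four stronger readings are tempting, and the documents do not support them.

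- *The plan says it deletes people without a week-12 score.* It does not. The exclusion is a property of the named method, and the text is silent on missing data.
- *Arm-specific, outcome-related loss is likely.* No dropout rate, reason or direction is given. Sessions are short and on site, the sponsor's previous trial of the intervention is reported as free of adverse events, and people without joint pain are eligible. Loss unrelated to outcome gives no bias, and control-arm loss could offset it.
- *The error rate rises to about 20%.* That needs exactly the 4 worst changers of 20 to leave the exercise arm and no control to leave. It is an extreme bound (0.33-0.35 SD).
- *The bias reaches the MCID.* That depends on an SD of 20. The plan does not say which SD standardises its effect size, and it may not be the SD of change.

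Recruiting 40 against 27 does not answer the point either. Extra participants add precision but do not remove selection.

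**Conclusion.** The point holds as a conditional one. The named analysis uses completers only, and the plan lacks both safeguards: collecting week-12 LEFS regardless of attendance and analysing by allocated arm. If scores are lost unequally and in relation to outcome, the primary contrast can be biased. The central illustration is a shift of about 0.17-0.24 SD and a two-sided error of about 8-11%. It rests on assumed loss of 20-30% in the exercise arm only, a correlation of 0.5, and no true effect. At 10% loss the error is 5.3-6.1%, which is of little consequence.

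A reader might also infer that a mixed model would solve the problem. With only two visits, a dropout contributes just a baseline score, so no model recovers the unseen week-12 value. Collecting the score is the main protection. The change is worth making before week-12 data are collected, but the documents do not show that material bias will occur.

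**What to change.** 1. **Collect and analyse everyone.** State that week-12 LEFS will be obtained from every randomised participant regardless of attendance, by e-mail, post or phone if the visit is missed, and that all 40 are analysed in the arm allocated.
2. **Adjust for baseline.** Replace the change-score ANOVA with ANCOVA of week-12 LEFS on arm and baseline, or with a constrained longitudinal model (baseline and week 12 as responses, common baseline mean, arm effect at week 12). Justify it by precision and by protection against baseline-related loss, and do not present it as a cure for loss that depends on the unseen score.
3. **Optionally, add a sensitivity analysis** giving exercise-arm participants with missing scores the control-arm change, labelled as a partial check.

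The cost is a few sentences of plan text and a few e-mails or calls, with no change to sample size or intervention. The downside is that a remotely completed LEFS differs slightly in setting from one completed at the visit, so the mode of completion should be recorded.
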